Statistical analyses will be performed using R software and IBM SPSS.

A total of 266 patients are planned for inclusion, divided into two balanced groups.

DESCRIPTION OF PLANNED STATISTICAL METHODS:

Research Protocol

Patients will be analyzed on an intention-to-treat basis and then per-protocol.

Intention-to-treat analysis: all patients included in the study for whom outcome data are available will be considered in the analysis according to their randomization group. No imputation method will be used in case of missing data.

If organizational constraints prevent the patient from receiving prophylactic NIV (despite inclusion in the corresponding intervention arm), the patient will remain in their randomization arm for the entire study duration, and their data will be analyzed on an intention-to-treat basis.

Per-protocol analysis excludes patients for whom the initial protocol was not fully adhered to. Only patients who followed the protocol will be considered in the analyses, within the arm to which they were originally randomized.

The analysis will focus on the primary endpoint to determine whether randomization to the "PPC prevention strategy" arm leads to a reduction in PPC frequency compared to the control group. Effect size and number needed to treat will be calculated.

Similarly, for secondary endpoints, significant differences between the two groups will be sought in terms of:

- a) Safety and tolerability of the strategy under study (see safety assessment parameters)
- b) Mortality during hospitalization
- c) Patient reintubation
- d) Length of stay and duration of invasive or non-invasive mechanical ventilation

Description of the overall analysis method

The significance threshold is set at 0.05, and all tests will be two-sided. For qualitative variables, results will be reported as counts and percentages. For quantitative variables, results will be reported as means and standard deviations in case of normal distribution, and as medians with 25th and 75th percentiles in the absence of a Gaussian distribution. Normality of continuous variables will be assessed using the Kolmogorov-Smirnov test.

A simple descriptive analysis will be performed on the entire study population and by subgroups. This description will include sociodemographic data, medical history, ongoing treatments, etc.

A qualitative and quantitative analysis of missing data will be performed. No imputation of missing data is planned for the endpoints.

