- Identification of factors associated with failure of prophylactic NIV in the subgroup where NIV was prematurely discontinued.

Statistical Justification for Sample Size:

Previously described data indicate that the expected effect size is approximately a 50% reduction in events:

- In studies on medical populations, the effect of prophylactic NIV was observed even on harder endpoints than ours: -66% reduction in reintubation, -51% reduction in ARF incidence, and -50% reduction in reintubations, and again -69% reduction in ARF incidence.

- In surgical populations, prophylactic NIV has led to a reduction in restrictive syndrome of about 50%, an improvement in pulmonary function tests (PFTs) of +30%, and a decrease in length of stay by 7 days.
- In curative use after abdominal surgery—a more unfavorable situation since ARF is more advanced—Squadrone reported favorable outcomes in 90% of cases with CPAP, and reintubations were reduced by 30%.

Given that the expected incidence of ARF in the high-risk group is 30–50%, a sample size of at least 121 subjects per arm is required to demonstrate, under a two-sided hypothesis, a relative reduction of 50% in ARF between a group managed with prophylactic NIV (15%) and a group managed with standard care (30%), with an alpha risk of 5% and a beta power of 90%. We anticipate 10% of patients will be non-evaluable.

The required sample size is therefore $242 + 24 = 266$ high-risk subjects evaluated for PPC.

STATISTICAL STOPPING RULES:

No interim analysis is planned in the protocol. However, if during the review of safety and efficacy data provided to the independent monitoring committee (raw, descriptive, and summarized data without pre-established statistics by the investigator or sponsor), a highly significant difference is identified for the primary endpoint or one of the safety parameters when comparing the two groups blinded to treatment allocation, the committee may decide to stop the study.

METHOD FOR HANDLING MISSING, UNUSED, OR INVALID DATA:

Patients included in the study for whom an endpoint is not available will not be considered in the analysis for that missing endpoint. No imputation method will be used for missing data.

MANAGEMENT OF CHANGES TO THE INITIAL ANALYSIS PLAN:

Modifications to the initial analysis plan may be proposed by the monitoring committee (interim analysis, statistical tests, adverse events, secondary objectives) if new literature data justify them.

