Protocol deviations will be identified and measured. Dual analysis—intention-to-treat and per-protocol—will assess the impact of protocol deviations on study results.

SELECTION OF PATIENTS FOR ANALYSIS:

All patients included in the study, meeting all inclusion criteria and presenting no exclusion criteria, will be included in the analyses of available endpoints according to their case report forms.

See Criteria for Premature Discontinuation of a Participant's Involvement in the Study:

- **Withdrawal of consent:** Data collected will not be included in the intention-to-treat analysis.
- **Discontinuation by the investigator:** Data already collected will be used in the analyses unless the subject withdraws consent.
- **Lost to follow-up:** Data collected for subjects lost to follow-up will be used in the analyses unless the subject withdraws consent.
- **Organizational impossibility to receive prophylactic NIV (inclusion in the corresponding intervention arm):** The patient will be included in the intention-to-treat analysis and followed under the same conditions as in the control arm.

RANDOMIZATION

High-risk patients with an ARISCAT score ≥ 45 will be randomized upon inclusion in the study during the preoperative period (consultation or pre-anesthesia visit, and no later than the day of surgery before anesthesia begins).

Treatment allocation will be performed through centralized computerized electronic randomization by minimization into two groups (1:1), with stratification by center, sex, age, preoperative SpO₂, presence of respiratory infection within the previous month, anemia, surgical incision (upper abdominal or intrathoracic), expected surgery duration (≤ 2 h, 2–3h, > 3 h), and procedure urgency.

F) Planned Duration of the Trial

Inclusion period:	30 months
Treatment period:	48 hours
Follow-up period:	7 days
Total duration of the trial (including follow-up):	30.5 months

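### The stated 90% power is about 80% at 121 per arm even with full NIV delivery, and the sample size makes no allowance for NIV-arm patients who get no NIV but stay in the intention-to-treat analysis

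*Combined protocol and SAP*

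**What the plan says.** All references are to part E of the combined protocol and SAP.

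- **Statistical Justification for Sample Size.** The trial is sized to "demonstrate, under a two-sided hypothesis, a relative reduction of 50% in ARF", comparing "a group managed with prophylactic NIV (15%) and a group managed with standard care (30"%). The error rates stand in the same sentence: "with an alpha risk of 5% and a beta power of 90"%. This is said to require at least 121 per arm. The only addition is 10% for non-evaluable patients: 242 + 24 = 266.
- **Description of planned statistical methods.** Patients are analysed by intention to treat and then per protocol. If organisational constraints prevent prophylactic NIV, "the patient will remain in their randomization arm for the entire study duration".
- **Selection of patients for analysis.** For the same patients: "The patient will be included in the intention-to-treat analysis and followed under the same conditions as in the control arm".
- **Overall analysis method.** "The significance threshold is set at 0.05, and all tests will be two-sided". Under the study of associations, the test for a binary variable is Pearson's chi-square or Fisher's exact test.

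No section gives an expected frequency of non-delivery. None says whether the 15% describes patients who receive NIV or all patients assigned to it.

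**The concern.** There are two separate problems with the power statement.

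The first does not depend on delivery at all. The figure of 121 per arm is what the standard formula returns for 80% power at these rates, not 90%.

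The second concerns the contrast being powered. Patients assigned to NIV who get none are followed like controls, so it is reasonable to expect roughly the control ARF rate in them. If the 15% is the rate among recipients, each such patient pulls the arm's rate towards 30% and shrinks the intention-to-treat difference. These patients still have an endpoint, so the 10% margin does not absorb them.

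At stake is how a non-significant result would be read. Someone who believes the trial had 90% power would take it as fairly strong evidence against a halving of ARF. With 80% power or less, that inference is weaker, and part of a null result could reflect NIV that was not delivered.

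**Working it through.** **Inputs from the plan.** Control rate p1 = 0.30; NIV rate p2 = 0.15; two-sided alpha 0.05 (z = 1.960); 1:1 allocation; n = 121 per arm; stated power 90%.

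**Assumptions, not in the plan.** f is the fraction of NIV-arm patients who receive no NIV, shown at 5%, 10% and 20%. Those patients have the control rate, and 15% is the rate in recipients.

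**Formula** (pooled variance under the null, without continuity correction), with p̄ = (p1 + p2)/2:

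z_power = [ |p1 − p2| √n − 1.960 √(2 p̄(1 − p̄)) ] / √( p1(1 − p1) + p2(1 − p2) )

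**Step 1: the plan's own figure, full delivery.** p̄ = 0.225, so √(2 × 0.225 × 0.775) = 0.5906. The denominator is √(0.21 + 0.1275) = 0.5809. The first term is 0.15 × √121 = 1.65.

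z_power = (1.65 − 1.960 × 0.5906)/0.5809 = 0.848, a power of **80.2%**.

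Solving for n gives 121 per arm at 80% power and **161 per arm** at 90%. Other variants do not rescue the claim. For 90% two-sided, the unpooled formula needs 158 per arm, the arcsine 159 and the continuity-corrected formula 174. Even a one-sided test needs 131, and 121 per arm gives 87.9% one-sided. The stated combination is therefore not reproduced, whereas 121 matches the two-sided 80% figure exactly.

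**Step 2: dilution.** The intention-to-treat rate in the NIV arm is 0.15(1 − f) + 0.30f = 0.15 + 0.15f.

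| f (assumed) | NIV-arm rate | Relative reduction | Power, 121 per arm | Gap to 90%: base error | Gap to 90%: dilution | n per arm for 80% | n per arm for 90% |
|---|---|---|---|---|---|---|---|
| 0 | 15.00% | 50.0% | 80.2% | 9.8 | 0 | 121 | 161 |
| 5% | 15.75% | 47.5% | 75.5% | 9.8 | 4.7 | 136 | 181 |
| 10% | 16.50% | 45.0% | 70.3% | 9.8 | 9.9 | 153 | 204 |
| 20% | 18.00% | 40.0% | 59.0% | 9.8 | 21.2 | 198 | 265 |

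Gaps are in percentage points: base error is 90 − 80.2, and dilution is 80.2 minus the power in that row.

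**Step 3: does the 10% margin help?** It is meant for missing endpoints. Even if none were missing and all 133 per arm (266/2) were analysed, power would be 83.8% at f = 0, 74.4% at f = 10% and 63.1% at f = 20%.

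**The case against.** The case against the dilution part is substantial; the base error in step 1 is not affected by it.

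- **What the 15% means.** A reader might infer that the power is calculated for an effect the analysis will not estimate. The documents do not establish that. The primary objective concerns a management strategy, and the analysis section asks about randomisation to the prevention-strategy arm. The 15% can be read as the rate in the assigned arm, which is what intention to treat estimates. This objection stands, and it is why the plan should say which rate is meant.
- **Possible slack in the 50%.** The sample-size section cites ARF reductions of 51% and 69% from earlier studies. If these are effects in recipients, a net 50% tolerates f = 1 − 50/69, about 28%, in one case and f = 1 − 50/51, about 2%, in the other. The plan does not say which applies, or whether those figures already include non-delivery. Slack is possible but not shown.
- **Frequency.** A reader might also infer that the plan expects appreciable non-delivery. It does not say so: the rule is worded as a contingency, and f may be small. At f = 2% the power is 78.3%, a loss of about 2 points.
- **Control rate.** The plan expects 30–50% and sizes at the bottom. At 40% with the same halving, 121 per arm gives 92.9% at f = 0, 86.2% at f = 10% and 76.4% at f = 20%. This is true, but the plan attaches its power claim to 30%.
- **Existing safeguards.** Deviations are to be identified and measured, and a per-protocol analysis is planned. This largely covers the reporting of non-delivery. It does not restore power for the intention-to-treat comparison, and per-protocol exclusions after randomisation give up the randomised balance.

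**Conclusion.** The power statement is wrong as written. At the plan's own inputs, 121 per arm gives about 80%, not 90%. That conclusion needs no outside assumption.

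The sample-size text also lacks any allowance for NIV-arm patients without NIV, or any reason why none is needed. The size of that effect is conditional. It requires that 15% is the recipient rate, that untreated patients have the control rate, and that f lies in the range shown. On those terms power is 75.5%, 70.3% or 59.0% at f = 5%, 10% or 20%. It would be a mistake to attribute the whole distance from 90% to dilution, since 9.8 points of it are the base error.

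Nor should anyone conclude that these patients ought to leave the intention-to-treat analysis. Retaining them is right; the gap is in the sample-size justification.

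**What to change.** In Statistical Justification for Sample Size:

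1. Restate the power as about 80% for 30% versus 15% with 121 evaluable patients per arm and full NIV delivery. If 90% is to be kept as the claim, the plan must acknowledge that this needs about 161 evaluable per arm (322 in total, or 322/0.9 = 358 with 10% non-evaluable).
2. Say in one sentence whether 15% is the rate among NIV recipients or in the whole assigned arm. If it is the latter, say what non-delivery it already allows for.
3. Add a short table of intention-to-treat power at f = 5%, 10% and 20%, with f labelled as an assumption.

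Leave the intention-to-treat rule unchanged.

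The cost is a few lines of text and a less favourable stated power.

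Confirming an NIV slot before allocation is optional and not part of this correction. Allocation is allowed up to a point "no later than the day of surgery before anesthesia begins", so there may be room for such a check. However, it would leave out patients on days without capacity, and the documents do not say when capacity becomes known.

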
- Death from any cause during hospitalization for surgery

Assessment of an effect on patient reintubation:

- Reintubation due to respiratory failure (ARF)
- Reintubation due to non-respiratory failure, excluding reintubations specifically for a new surgical or interventional radiology procedure
- Time to reintubation to assess delayed reintubation (characterized by a non-significant difference in reintubation rate between groups but a longer delay in the NIV group)

Assessment of an effect on length of stay in ICU and duration of invasive or non-invasive mechanical ventilation:

- Number of days of invasive mechanical ventilation (intubated or tracheostomized) during hospitalization for surgery, including episodes of reintubation
- Number of days of non-invasive mechanical ventilation (NIV) during hospitalization for surgery, including prophylactic and therapeutic NIV.

**Assessment of an effect on the incidence of healthcare-associated infections, defined according to
Centers for Disease Control (CDC) criteria:**

- Infectious pneumonia: see secondary endpoint criteria
- Urinary tract infection: fever $> 38^{\circ}\text{C}$ and urine culture showing no more than two microbial species, at least one with a concentration $> 10^5 \text{ CFU/ml}$, in a patient with no other obvious source of infection
- Catheter-related infection: fever $> 38^{\circ}\text{C}$, positive catheter culture or sample, and resolution of fever within 48 hours after catheter removal without antibiotic change and no other identified source of infection
- Bacteremia: fever $> 38^{\circ}\text{C}$ and at least one positive blood culture (two or more if coagulase-negative staphylococcus)
- Surgical site infection

Data collection is performed prospectively throughout the first 7 days of hospitalization for surgery.

D) Description of Investigational Medicinal Products

MEDICAMENTS :

Name of the Medicinal Product (INN)	Brand Name	Pharmaceutical Form	Route of Administration	Dosage per Administration
Medical Liquid Oxygen	N/A	Gas	N/A	

Therapeutic regimen:

The ventilatory mode used will be an assisted mode (PSV or BiPAP), as these have shown a stronger (86) and more sustained effect (29) than CPAP alone.

The interface—nasal mask, face mask, or helmet—is chosen according to the unit's usual practice.

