Study of Associations (Qualitative and/or Quantitative Variables):

For each parameter of interest, a bivariate analysis will be performed, possibly complemented by a multivariate analysis adapted to the outcome variable to explore potential associations.

For bivariate analyses, the use of parametric or non-parametric tests will depend on sample size and/or variable distribution. The significance threshold is set at 0.05, and all tests will be two-sided.

The statistical test used will be Pearson's Chi-square test (or Fisher's exact test) for qualitative variables. For quantitative variables, the statistical tests used will be ANOVA or the non-parametric Kruskal-Wallis test.

The association between each presumed risk factor and the parameter of interest will be estimated using the relative risk (RR) and its 95% confidence interval.

A multivariate logistic regression analysis will estimate the adjusted RR and its 95% confidence interval for each retained factor (conservative threshold of 0.20 in univariate analysis).

Early Mortality:

Overall survival is defined as the time between the date of operating room discharge and the date of death if the patient dies within 7 days, or the end of study follow-up at Day 7. The Kaplan-Meier method will be used to estimate survival rates and plot survival curves. The Log-Rank test will be used to compare survival curves. Event-free survival is defined as the time between operating room discharge and the date of occurrence of the event (PPC) or the date of last follow-up if censored.

A semi-parametric Cox proportional hazards regression model will estimate for each variable the crude association (Hazard Ratio, HR) between the factor studied and death (bivariate analysis), then the adjusted HR in multivariate analysis.

The significance threshold for including other variables in the multivariate analysis will be 0.20. If several candidate variables are redundant, the most representative variable will be retained for the model.

Subgroup Analyses (Exploratory):

Subgroup analyses will address the occurrence of endpoints:

- According to patient characteristics at inclusion (medical history, ARISCAT score components, type of surgery, and planned anesthetic technique).
- The subgroup of patients receiving NIV as curative (under conditions noted at session start) will be compared to the group receiving NIV only prophylactically in terms of outcome at Day 7.

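### Allocation is minimised on centre and eight other factors, but the only test named for ARF ignores them: the test is conservative and gives up a modest, assumption-dependent amount of power

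*Combined protocol and SAP*

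**What the plan says.** All references are to the combined protocol and SAP.

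- **Randomization (section E).** Allocation is 1:1 by centralised minimisation, "with stratification by center, sex, age, preoperative SpO₂, presence of respiratory infection within the previous month, anemia, surgical incision", expected duration of surgery in three bands, and urgency. That is centre plus eight factors. The synopsis expects three centres.
- **Study of Associations (section E).** "The statistical test used will be Pearson's Chi-square test (or Fisher's exact test) for qualitative variables". A multivariable analysis may be added to explore associations. It is a logistic regression giving an adjusted relative risk "for each retained factor (conservative threshold of 0.20 in univariate analysis").
- **Description of planned statistical methods (section E).** This sets intention-to-treat and then per-protocol analysis of the primary endpoint, with an effect size and number needed to treat. It names no model and no covariates.
- **Level of the tests.** "The significance threshold is set at 0.05, and all tests will be two-sided".

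Nothing requires centre or any other minimisation factor to enter the ARF comparison, and nothing says which result is primary if both an unadjusted and an adjusted one are produced.

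**The concern.** Minimisation forces the arms to resemble each other on the chosen factors. If those factors predict ARF, part of the chance difference between arms that would occur under simple randomisation has been removed. The chi-square does not know this. Its standard error still counts that variation as noise and is therefore too large. The test rejects less often than its nominal 5% under the null, and some of the precision that minimisation could deliver is left unused.

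The optional model does not settle the matter. Its covariates are chosen by their p-values in the trial's own data, so the adjusted estimate depends on which factors happen to pass 0.20, and a factor that governed allocation can drop out.

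**Working it through.** **1. The plan's own sample size, as the baseline for power.** Inputs from Statistical Justification for Sample Size: ARF 30% against 15%, two-sided 5%, 121 evaluable per arm. With the pooled two-proportion formula, mean rate 0.225:

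n = [1.960 × √(2 × 0.225 × 0.775) + z × √(0.30 × 0.70 + 0.15 × 0.85)]² / 0.15²

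- 80% power (z = 0.842): (1.1575 + 0.4889)² / 0.0225 = 120.5, so 121.
- 90% power (z = 1.282): (1.1575 + 0.7445)² / 0.0225 = 160.8, so 161.
- Power at 121 per arm: Φ[(0.15 × √121 − 1.1575) / 0.5809] = Φ(0.848) = 80.2%.

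The stated 90% is not reproduced, and 121 is the 80% figure. So power below should be read against 80.2%.

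**2. Expected size by hand.** If the factors explain a share R² of outcome variance and balance is perfect, the true variance of the difference under the null is (1 − R²) times what the chi-square assumes. Its type I error is then 2 × [1 − Φ(1.96 / √(1 − R²))]:

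- R² = 5%: critical value 2.011, type I error 4.4%
- R² = 12%: 2.089, 3.7%
- R² = 22%: 2.219, 2.6%

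These R² values are assumptions.

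**3. Simulation.** N = 242, control ARF 30%, NIV 15% (or 30% under the null), minimisation on nine factors with a 0.8 biased coin, 14 covariate terms, 10,000 trials per scenario. Factor prevalences, effects and the coin probability are assumptions, because the plan gives none. SD is the assumed standard deviation of the prognostic log-odds. The Monte Carlo standard error is about √(0.05 × 0.95 / 10,000) = 0.2 points for type I error and √(0.8 × 0.2 / 10,000) = 0.4 points for power.

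| SD | Chi-square type I | Chi-square power | Standardised risk difference, power | Logistic LR test, power |
|---|---|---|---|---|
| 0.41 | 4.7% | 81.0% | 82.1% | 83.0% |
| 0.83 | 4.1% | 82.1% | 85.4% | 86.3% |
| 1.24 | 3.2% | 82.7% | 88.6% | 89.1% |

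With non-prognostic factors the chi-square holds its level (4.9%). The gain for the standardised estimator is 1.1, 3.3 and 5.9 points.

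**4. Allowing for the size of the adjusted test.** In step 3 the logistic likelihood-ratio (LR) test was slightly liberal, at 5.7% to 6.5%, and the standardised estimator ran at 5.1% to 6.0%. Part of the raw gain is therefore not real. A further simulation (4,000 trials per scenario, age and SpO₂ as single ordinal terms) corrected the LR test to a true 5%:

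- SD 0.41: 80.9% to 81.4%, a gain of 0.5 points
- SD 0.83: 81.9% to 83.5%, 1.6 points
- SD 1.24: 82.2% to 88.0%, 5.8 points

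**5. Centre alone.** With only centre prognostic (log-odds 0, +0.4, −0.4), the chi-square type I error is 4.9%, and adjusting for centre moves power from 79.8% to 80.5%, under 1 point.

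**6. The 0.20 screen (4,000 trials per scenario).** At SD 0.83 the screened model had 84.2% power against 84.9% for the full model, so little power is lost. Across the scenarios centre was retained in only about 30% to 79% of trials, so the adjustment set is unstable.

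**7. Events against terms.** Expected events: 121 × 0.30 + 121 × 0.15 = 36.3 + 18.15, about 54. With age and SpO₂ as single terms: centre 2, sex 1, age 1, SpO₂ 1, infection 1, anaemia 1, incision 1 or 2, duration 1 or 2, urgency 1, giving 10 to 12. With 12 plus treatment, 54 / 13 is about 4 events per parameter.

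**The case against.** The strongest reply is that the planned test is safe. A conservative test creates no extra false positives, and its simulated power of 81.0% to 82.7% in step 3 is not below the 80.2% that 121 per arm buys. Power is given up only relative to a better analysis, whereas the full logistic LR test errs slightly in the less welcome direction. The size rests on prognostic strength that the plan does not state, and enrolling only patients with ARISCAT of 45 or more may narrow the spread of risk. All of this stands. It limits the size of the point but does not answer it: the plan still leaves the adjustment of its primary comparison undecided.

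Four stronger readings are tempting, and the documents do not support them.

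- *The error rate is inflated.* It is not; the departure is downwards.
- *Failure to adjust explains why the trial misses its stated power.* The sample size is justified "with an alpha risk of 5% and a beta power of 90" per cent, but step 1 shows that 121 per arm is an 80% sample size. That is a separate error.
- *NIV delivery is left to each unit, so centre must be modelled.* The interface "is chosen according to the unit's usual practice" and the timetable may be adapted locally, but Therapeutic regimen and Duration of Treatment set the ventilatory mode, pressure ranges, session length and daily duration. A centre main effect would not in any case address differences between centres in the treatment effect.
- *The 0.20 screen governs the primary test.* It applies only to the optional exploratory model; the chi-square never uses it.

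**Conclusion.** The point holds as a modest one. The design balances on nine factors, and the only named ARF test uses none of them. If the factors are prognostic, that test has a type I error of about 3% to 4.7% and gives up roughly 0.5 to 6 points of power. The upper end needs strongly prognostic factors (SD about 1.24). With weak factors, or if only centre matters, the effect is negligible. The direction follows from the design; the size rests on assumed factor effects, prevalences and a 0.8 coin, so confidence in the magnitude is moderate. The lack of a single named primary analysis, and a covariate set that depends on the data, are weaknesses whatever the strength of the factors. The trial remains valid without the change. It is worth making because it recovers some power without recruiting anyone.

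**What to change.** In the SAP:

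1. Define the primary intention-to-treat ARF comparison as one pre-specified model with treatment, centre and the other eight minimisation factors, entered regardless of p-value.
2. Code parsimoniously, with age and SpO₂ as continuous or single ordinal terms.
3. Report a standardised (marginal) risk difference and risk ratio with 95% confidence intervals. This also supplies the adjusted relative risk that the plan expects from a logistic regression, which yields odds ratios directly.
4. Keep the unadjusted chi-square as a supporting analysis, and optionally a re-randomisation test that repeats the minimisation.
5. Do not apply the 0.20 screen to the minimisation factors.

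The cost is wording and a few lines of code, since the factors are already needed for allocation. The downside is 10 to 12 covariate terms against about 54 events, which can make a logistic LR test slightly liberal (about 5.3% to 6.5% across the simulations). The standardised estimator with sparse coding is preferred for that reason. It was itself simulated only with 14 terms (5.1% to 6.0%), so the re-randomisation test is a useful check.
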